### **ALS Functional Rating Scale – Revised (ALSFRS-R) Questionnaire**

---

#### **CONFIDENTIAL INFORMATION**

The information in this study protocol is confidential. Any disclosure, copying or distribution of the information contained within is strictly prohibited without written consent from University of Florida.

The ALSFRS-R is a quickly administered (5 minute) ordinal rating scale (ratings 0-4) used to determine subjects' assessment of their capability and independence in 12 functional activities/questions (Cedarbaum, 1999). All 12 activities are relevant in ALS. Initial validity was established by documenting that in subjects with ALS, change in ALSFRS-R scores correlated with change in strength over time, was closely associated with quality of life measures, and predicted survival (**Appendix A**). The test-retest reliability is greater than 0.88 for all test items. The advantages of the ALSFRS-R are that the categories are relevant to ALS; it is a sensitive and reliable tool for assessing activities of daily living function in subjects with ALS; and it is quickly administered. In a recent trial employing the ALSFRS as a secondary outcome measure, placebo-treated patients showed a decline of 0.92 units per month, with a standard error of 0.08. With appropriate training the ALSFRS-R can be administered with high inter-rater reliability and test retest reliability.

**Beck Depression Inventory-Fast Screen (BDI-FS) (Appendix D)** is a brief self-report inventory designed to evaluate depression in patients with medical illness. It has been found to be an efficient and effective tool for depression screening in the ALS population. The symptoms and prognosis of ALS have an immense impact on a patient's life as well as their family and caregivers. Depression, when present, can significantly affect the life of patients and is more commonly seen in situations involving the threat of loss. BDI-FS is a short 7 question self-report that can assist the investigator and staff in evaluating if patients are dealing with depression. The BDI-FS is evaluated at the time of the subject's study visit by study staff. Each answer is scored on a scale of 0-3. Measures of 4-6 correspond to mild depression, 7-9 indicate moderate depression, and 10-21 indicates moderate-severe depression. Any measurement indicating depression, or any verbal suggestion of suicidality, will be reported to the investigator immediately. The investigator will address the results with the subject prior to their leaving the facility. Any interventions deemed necessary will be addressed by a qualified physician or investigator at that time.

### **12.2.2. On-Study/On-Intervention Evaluations/Procedures**

#### **12.2.2.1. Baseline, Visit 1, Day 1 pm and Visit 1, Day 2 am:**

The baseline visit (Visit 1, Day 1 pm and Visit 1, Day 2 am), will cover 2 days and include the first dose of study drug, and study drug dispensing. It will be scheduled within 14 to 28 days after the screening visit. At this visit inclusion/exclusion criteria and concomitant medications will be reviewed. Vital signs, brief physical and neurologic examination, as well as study questionnaires and testing will be performed as noted in the schedule of activities. To lessen travel for participants during the COVID-19 pandemic, and after the pandemic, the Visit 1, Day 1 and Visit 1, Day 2 may take place in the same week as the Screening visit. If these visits are scheduled to take place in the same week, the \*clinical labs for safety and \*blood draw for C9+ and RAN proteins, and \*urine pregnancy test, will not be repeated.

The following documentation and procedures will be performed at Baseline (Visit 1, Day 1):

---

#### **CONFIDENTIAL INFORMATION**

The information in this study protocol is confidential. Any disclosure, copying or distribution of the information contained within is strictly prohibited without written consent from University of Florida.

- FOIS
- BDI-Fast Screen (BDI-FS)
- VFSS – Penetration Aspiration Scale
- EAT – 10
- Forced Vital capacity (FVC)
- Peak Cough Flow
- Body Mass Index

The following documentation and procedures will be performed at Baseline (Visit 1, Day 2):

- Adverse event review
- Inclusion/exclusion assessment
- Record/review Concomitant medications
- Medical history
- Vital signs; weight and height
- Brief physical exam
- Brief neurologic exam
- Clinical labs for safety (hematology, chemistry, liver functions, and urinalysis)
- Blood draw for C9+ and RAN proteins
- Lumbar puncture for RAN proteins and biomarkers
- Urine Pregnancy Test (females of childbearing potential)
- MRI/DTI imaging
- ALSFRS-R
- Dispense study drug

### **Eating Assessment Tool -10 (EAT-10)**

EAT-10: The Eating Assessment Tool-10, is a validated 10-item patient report scale of perceived swallowing impairment (Belafsky et al. 2008). The EAT-10 uses a 5-point ordinal rating scale where a patient rates their perceived degree of impairment for each item from 0 (no impairment) to 4 (severe impairment) for a total range of scores between 0 (no perceived swallowing impairment) to 40 (severe impairment) (**Appendix B**). One of the former PIs of this study ([name]) recently determined that the EAT-10 was sensitive to identify ALS patients with severe dysphagia including aspiration. A Receiver Operating Curve analysis revealed that a cut point of 8 on the EAT-10 yielded a sensitivity of 86%, specificity of 72%,

---

#### **CONFIDENTIAL INFORMATION**

The information in this study protocol is confidential. Any disclosure, copying or distribution of the information contained within is strictly prohibited without written consent from University of Florida.

likelihood ratio of 3.1, and negative predictive value of 95.5% for detecting aspiration in ALS ([name], et al., 2016).

#### **Functional Oral Intake Scale (FOIS)**

The FOIS is a simple 7-point scale (Crary, 2005 – see **Appendix C**) that describes the subject's functional status with respect to oral intake, ranging from 1 (No oral intake) to 7 (total oral intake with no restrictions).

#### **12.2.2.2. Study Visit 2, Week 6:**

All subjects will return at week 6 for a brief evaluation. The visit window is to be scheduled at 6 weeks (42 days) plus or minus 3 days. Participants will be seen for assessment of any adverse events, and concomitant medications. Study drug accountability and compliance will be assessed. Vital signs, brief physical and neurologic examination, as well as study questionnaires and testing will be performed as noted in the schedule of activities.

The following procedures will be performed at Visit 2, Week 6:

- Adverse events review
- Record/review Concomitant medications
- Vital signs, weight and height
- ALSFRS-R
- Brief physical exam
- Brief neurologic exam
- Clinical labs for safety (hematology, chemistry, liver functions, and urinalysis)
- Blood draw for C9+ and RAN proteins
- Lumbar puncture for RAN proteins and biomarkers
- Dispense study medication
- Drug Accountability/Compliance
- BDI-Fast Screen (BDI-FS)
- Urine Pregnancy Test (females of childbearing potential)

#### **12.2.2.3. Study Visit 3, Week 12:**

All subjects will return at week 12 for a mid-study evaluation. The visit window is to be scheduled at 12 weeks (84 days) plus or minus 3 days. Participants will be seen for assessment of any adverse events, and concomitant medications. Study drug accountability and compliance will be assessed. Vital signs, physical and neurologic examination, as well as study questionnaires and testing will be performed as noted in the schedule of activities.

The following procedures will be performed at Visit 3, Week 12:

---

#### **CONFIDENTIAL INFORMATION**

The information in this study protocol is confidential. Any disclosure, copying or distribution of the information contained within is strictly prohibited without written consent from University of Florida.

- Adverse events review
- Record/review concomitant medications
- Vital signs, weight and height
- ALSFRS-R
- Comprehensive physical exam
- Comprehensive neurologic exam
- Clinical labs for safety (hematology, chemistry, liver functions, and urinalysis)
- Blood draw for C9+ and RAN proteins
- Urine Pregnancy Test (females of childbearing potential)
- COVID-19 nasal collection and testing may take place at this visit if travel time allows for the participant - Due to COVID-19 Pandemic, nasal collection and testing of the participants has been implemented to determine if the participant is COVID negative. The collection is done at UF Springhill collection site and testing is completed at Rocky Point Labs overnight with results placed in EPIC. The results of the testing will be provided to the participant once results are posted in EPIC. This collection and testing may continue throughout participation in the study at this visit.
- Lumbar puncture for RAN proteins and biomarkers
- FOIS
- VFSS – Penetration Aspiration Scale
- EAT – 10
- Forced Vital capacity (FVC)
- Peak Cough Flow
- Body Mass Index
- BDI-Fast Screen (BDI-FS)
- Dispense study medication
- Drug Accountability/Compliance

#### **12.2.2.4. Phone Call, Week 18:**

Subjects will be contacted by phone at Week 18 and the following study related evaluations will be completed:

- ALSFRS-R
- EAT-10
- FOIS

---

#### **CONFIDENTIAL INFORMATION**

The information in this study protocol is confidential. Any disclosure, copying or distribution of the information contained within is strictly prohibited without written consent from University of Florida.

- Adverse event review
- Record/review concomitant medications

#### **12.2.2.5. Study Visit 4, Week 24 Day 1 or Day 2:**

All subjects will return at week 24 for a two-day end of study evaluation. The visit window is to be scheduled at 24 weeks (168 days) plus or minus 3 days. Participants will be seen for assessment of any adverse events, and concomitant medications. Study drug accountability and compliance will be assessed. Vital signs, physical and neurologic examination, as well as study questionnaires and testing will be performed as noted in the schedule of activities.

The following documentation and procedures will be performed at Visit 4, Week 24, on Day 1 or Day 2:

- Adverse events
- Record/review concomitant medications
- Vital signs, weight and height
- ALSFRS-R
- Comprehensive physical exam
- Comprehensive neurologic exam
- Clinical labs for safety (hematology, chemistry, liver functions, and urinalysis) – Due to the COVID-19 Pandemic, and only for the participants currently enrolled (3) in this study, the clinical labs for safety will be drawn at a local lab or physician's office and will be shipped as needed. If there is any charge for the draw the participant may either pay the invoice and be reimbursed or have the lab contact the study team in the ICF to pay the invoice directly. This modification to the protocol is to prevent potential exposure to COVID-19 by minimizing participant travel to our site.
- Blood draw for C9+ and RAN proteins – Due to the COVID-19 Pandemic, and only for the participants currently enrolled (3) in this study, additional blood samples will be collected and will be shipped to the [name] Lab for analysis. The kits, drawing instructions, and shipping documents will be sent to the physician or the participant to complete this procedure. If there is a charge for the blood draw the participant may either pay the invoice and be reimbursed or have the lab contact the study team in the ICF to pay the invoice directly. This modification to the protocol is to prevent potential exposure to COVID-19 by minimizing participant travel to our site.
- Urine Pregnancy Test (females of childbearing potential)
- COVID-19 nasal collection and testing may take place at this visit if travel time allows for the participant - Due to COVID-19 Pandemic, nasal collection and testing of the participants has been implemented to determine if the participant is COVID

---

#### **CONFIDENTIAL INFORMATION**

The information in this study protocol is confidential. Any disclosure, copying or distribution of the information contained within is strictly prohibited without written consent from University of Florida.

negative. The collection is done at UF Springhill collection site and testing is completed at Rocky Point Labs overnight with results placed in EPIC. The results of the testing will be provided to the participant once results are posted in EPIC. This collection and testing may continue throughout participation in the study at this visit.

- Lumbar puncture for RAN proteins and biomarkers – Due to the COVID-19 Pandemic, and only for the participants currently enrolled (3) in this study, this procedure may be completed in the participant's home area and the samples shipped to the [name] Lab for analysis. The procedure will be completed by a licensed physician who is qualified in the proper procedures and has agreed to complete the lumbar puncture per the protocol. The lumbar puncture kit and needle will be shipped to the physician for this procedure. This modification to the protocol is to prevent potential exposure to COVID-19 by minimizing participant travel to our site.
- Drug Accountability/Compliance
- FOIS
- VFSS – Penetration Aspiration Scale
- EAT – 10
- Forced Vital capacity (FVC)
- Peak Cough Flow
- Body Mass Index
- BDI-Fast Screen (BDI-FS)
- MRI/DTI imaging

#### **12.2.2.6. Phone call, Week 36:**

Subjects will be contacted by phone at Week 36 and the following study related evaluations will be completed:

- Adverse events review
- Record/review concomitant medications
- ALSFRS-R
- EAT – 10
- FOIS

#### **12.2.2.7. Phone call, Week 52 (Follow-up):**

Subjects will be contacted by phone at week 52 for an end of study evaluation. The phone call window is to be scheduled at 52 weeks plus or minus 3 days.

- Adverse events review

---

#### **CONFIDENTIAL INFORMATION**

The information in this study protocol is confidential. Any disclosure, copying or distribution of the information contained within is strictly prohibited without written consent from University of Florida.

- Record/review concomitant medications
- ALSFRS-R
- EAT – 10
- FOIS

*Missed Visits:* If a subject fails to appear for a scheduled visit, the site will contact the subject. The site will stress the importance of the evaluation and reschedule within a window of +/- 3 days if possible.

#### **12.2.2.8. Study Medication/Intervention Discontinuation Evaluations/Procedures**

The investigator must document within 24 hours any subject permanently discontinuing study drug, documenting the reasons for discontinuation in the CRF and on the appropriate source documents. Subjects will be asked to comply with end of study assessments (visit 4 on schedule of activities table) at a follow-up visit in an outpatient setting (to be determined by Investigator or Staff) at 14 +/- days after the last treatment dose. The outcome measures will be documented at the study visit(s) following discontinuation of study drug. Subjects who have discontinued study drug will be removed from ongoing participation in the study.

Inclusion in the study is entirely voluntary and subjects may withdraw at any time for any reason. Possible reason for withdrawal could include serious adverse events, adverse events, and subject's choice. Subjects wishing to stop medication will immediately discontinue test drug. Subjects who elect to discontinue medication will be asked to comply with end of study assessments (visit 4 on schedule of activities table) at a follow up visit in an outpatient setting (to be determined by Investigator or Staff) at 14 +/- days after the last treatment dose.

Subjects who withdraw due to an adverse event will be followed whenever possible until resolution of the adverse event. It may be appropriate for the subject to return to the site 2 weeks after the subject is off study to evaluate for resolution of any adverse events and to receive further information about options for future clinical care. The Investigator will decide the course of action.

All serious adverse events (SAEs), whether or not the event is deemed drug-related, will be reported on the SAE Report Form.

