### CONFIDENTIAL INFORMATION

The information in this study protocol is confidential. Any disclosure, copying or distribution of the information contained within is strictly prohibited without written consent from University of Florida.

Study Duration	The anticipated time from study enrollment until completion of data collection and analyses is approximately 10-18 months.
Participant Duration:	Total study participant time is expected to be approximately 26 weeks from time of screening to completion of study trial phase and then an additional 26 weeks of follow-up phase (total 52 weeks).
Study Population and Sample Size	Approximately sixteen (16) subjects with C9orf72 ALS will be enrolled. The inclusion criteria are intended to provide a cohort of subjects with ALS who are appropriate candidates for treatment with Metformin. Subjects must be suitable candidates in the investigator's judgment and fulfill Inclusion/Exclusion criteria. Inclusion will require a diagnosis of probable, or definite ALS in accordance with the Revisited El-Escorial Criteria (Cedarbaum, 1999), positive testing for the C9orf72 expansion mutation, no allergies or contraindications to barium, Metformin, or inactive ingredients * in the study medication, and no contraindications to study procedures. Female subjects must not be pregnant or breast-feeding.
Phase	2

---

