#### **12.2.2.10. Off-Study Requirements**

Study medication will be distributed at Week 24 (due to COVID-19 pandemic and travel difficulties). Drug will be discontinued and collected at Week 36. Study drug will be ordered by the Co-Investigator, dispensed by Investigational Drug Service and a study team member will ship it to the participants (3). There are no additional risks of extending the medication by 12 weeks. The subject will be contacted by phone at weeks 18 and 36 to evaluate for resolution of any adverse events and to receive further information about options for future clinical care. In addition to this contact there will be another phone contact at weeks 36 and 52 to monitor long term health and follow-up on clinical outcome. This phone call will be at the discretion of the Investigator. Subjects may be contacted for follow-up safety evaluations, including possible blood draw for further study.

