## **14. CRITERIA FOR INTERVENTION DISCONTINUATION**

Subjects will be discontinued from the study under the following circumstances:

- If the subject is hemodynamically unstable
- If discontinuation suspension is recommended by treating physician
- At the subject's request

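### The plan does not settle whether scheduled phone follow-up continues after a subject stops metformin, and it gives three rules for the stopper's end visit

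*Combined protocol and SAP*

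**What the plan says.** **After stopping drug.** Section 12.2.2.8 says "Subjects who have discontinued study drug will be removed from ongoing participation in the study". The sentence just before it says "The outcome measures will be documented at the study visit(s) following discontinuation of study drug". Stoppers are asked to attend one end-of-study visit with the Visit 4 assessments.

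**Off-study contact.** Section 12.2.2.10, headed Off-Study Requirements, says "The subject will be contacted by phone at weeks 18 and 36 to evaluate for resolution of any adverse events". It adds "another phone contact at weeks 36 and 52 to monitor long term health and follow-up on clinical outcome", and then "This phone call will be at the discretion of the Investigator", without saying which call is meant. It also allows further safety contacts, possibly with a blood draw. It does not say whether early stoppers are included.

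**Planned duration.** The Synopsis (Participant Duration) counts a 26-week follow-up phase as part of a 52-week participation. Sections 12.2.2.4, 12.2.2.6 and 12.2.2.7 describe the week 18, 36 and 52 calls for subjects generally. Each call includes adverse events, ALSFRS-R, EAT-10 and FOIS.

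**Stopping drug versus leaving the study.** Section 14 is titled as criteria for discontinuing the intervention, but it opens "Subjects will be discontinued from the study under the following circumstances".

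**Timing of the stopper's end visit.** Sections 12.2 and 12.2.2.8 set it at "14 +/- days after the last treatment dose". The withdrawal text at the end of Section 9.1.2 counts 14 days from the last treatment visit. Section 12.2.2.9 counts 7 days from the last treatment visit.

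**The concern.** Stopping treatment and leaving the study are different events, and the plan does not keep them apart. Safety and tolerability is the primary objective, and Section 13 singles out adverse events that lead to permanent discontinuation. The outcome list under Table 3 names ALSFRS-R as the primary outcome measure. Subjects who stop are likely to differ from those who continue. If their scheduled contacts end at the end visit, every later summary of adverse events, ALSFRS-R, EAT-10 and FOIS describes only subjects who did not stop early.

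The end-visit conflict is a separate matter. One visit, with one set of assessments, has three timing rules, so two stoppers with the same history could be assessed at different times after their last dose.

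**Working it through.** The plan states no figure on this point to reproduce. Section 15.4 gives only a screening yield (50 screened for 16 enrolled).

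**1. Which text governs a stopper?**

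- *Reading A: the removal sentence in Section 12.2.2.8 governs.* The stopper has the requested end visit and then no scheduled contact.
- *Reading B: Section 12.2.2.10 governs.* The stopper leaves the on-study visits but still receives calls. In favour of this, on the 24-week plan only an early stopper could be off study at week 18. Against a clean reading, the same section also covers participants kept on drug from week 24 to week 36, makes a call discretionary, and does not name ALSFRS-R, EAT-10 or FOIS.

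No section says which reading applies.

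**2. What the two readings leave, for a stop at week 10**

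Inputs from Table 3: post-baseline ALSFRS-R and adverse-event assessments at weeks 6, 12, 18, 24, 36 and 52 (six); EAT-10 and FOIS at weeks 12, 18, 24, 36 and 52 (five). Assumption: the end visit is attended 14 days after the last dose, at week 10 + 2 = 12, and replaces the remaining clinic visits.

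| | Before stop | End visit | Reading A | Calls at weeks 18, 36, 52 | If all calls are made with the scales |
|---|---|---|---|---|---|
| ALSFRS-R, adverse events | 1 | 1 | 2 of 6 | 3 | 5 of 6 |
| EAT-10, FOIS | 0 | 1 | 1 of 5 | 3 | 4 of 5 |

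Under Reading A, scheduled observation ends 52 − 12 = 40 weeks before week 52. The last column is the most that Reading B can deliver, because the section leaves a call to discretion and does not name the scales.

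**3. The end-visit rules**

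Let D be the day of the last dose, V the day of the last treatment visit, and k = D − V.

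- Sections 12.2 and 12.2.2.8: D + 14
- Section 9.1.2: V + 14 = D + 14 − k
- Section 12.2.2.9: V + 7 = D + 7 − k

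The two visit-anchored rules differ by 14 − 7 = 7 days whatever k is. If the last treatment visit falls on the day of the last dose (k = 0), a stop on day 140 gives days 154, 154 and 147. If that visit came earlier (k > 0), the spread is k + 7 days. The term is not defined, so k is not fixed by the plan.

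**4. Is a stopper likely?**

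The plan gives no expected number of stoppers. With n = 16 and an assumed stopping probability p, the chance of at least one is 1 − (1 − p)^16. Section 6.4 cites a 6% discontinuation rate for diarrhea alone. Using 6% as an assumption gives 1 − 0.94^16 = 63%. Assumed rates of 10%, 20% and 30% give 81%, 97% and 99.7%.

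**The case against.** The strongest reply is that Reading A is not the natural one. Taken literally, the removal sentence would also remove every completer when drug ends, which the 52-week participation contradicts. The optional plural in "The outcome measures will be documented at the study visit(s) following discontinuation of study drug" may only reflect that Visit 4 spans two days. Section 12.2.2.10 then supplies the next step, and its week-18 contact points towards calling stoppers. This stands to a large extent: the 2-of-6 count applies only if the removal sentence overrides Section 12.2.2.10. What remains is that the plan does not say so, the named scales are not secured, and a call is discretionary.

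A reader might infer that stoppers are lost altogether. The documents do not support that. The stop and its reason are recorded within 24 hours, one end visit is requested, subjects who withdraw because of an adverse event are followed whenever possible until it resolves, and further safety contacts are allowed. These are kept on either reading.

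It can also be said that late calls tell little about tolerability. Fourteen days is 14 × 24 = 336 hours, or 336 / 17.6 ≈ 19 of the longer half-life in Section 6.3, and the week-52 call is off drug for everyone. That is fair. The loss would fall mainly on longer-term descriptive ALSFRS-R, EAT-10 and FOIS data, and Section 15.7 plans no efficacy analysis.

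On the end visit, a reader might infer that the visit-anchored rules place it weeks before the stop, by counting from the last scheduled clinic visit. No site could carry that out, and the undefined term does not require it. The blank after the plus-or-minus sign may have been lost when the file was converted to text, so it is not counted as a defect.

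**Conclusion.** The point holds as an unresolved conflict between sections. It does not show that the plan abandons subjects who stop. If Section 12.2.2.8 governs, a stop at week 10 leaves 2 of 6 ALSFRS-R and adverse-event assessments instead of 5 of 6, and later summaries cover only subjects who did not stop early. If Section 12.2.2.10 governs, most of that loss disappears, but the scales and the calls are not guaranteed. The counts assume an attended end visit 14 days after the last dose.

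The end-visit rules conflict by at least 7 days under any meaning of last treatment visit, and by more if it means the last scheduled clinic visit. No test or stated figure changes, because the analysis is descriptive. The matter should be corrected, since the change is small and it decides which subjects the follow-up summaries describe.

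**What to change.** 1. Replace the removal sentence in Section 12.2.2.8 with, for example: *Subjects who stop study drug remain in data collection for the remaining scheduled phone contacts (weeks 18, 36, 52) unless they withdraw consent.* Make Sections 12.2.2.10 and 14 agree. Section 12.2.2.10 should say whether its calls are scheduled or discretionary and that they include the adverse-event review, ALSFRS-R, EAT-10 and FOIS. Section 14 should separate stopping drug from leaving the study.
2. Reconcile the anchor and the number of days for the stopper's end visit across Sections 9.1.2, 12.2, 12.2.2.8 and 12.2.2.9, and define last treatment visit if the term is kept. Which timing is right is for the sponsor to decide.

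Cost: wording changes in six sections, IRB review under Section 16.3, possible re-consent under Section 16.3(a), and at most three phone calls per stopper. No new visit, procedure or variable is needed.
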